Chronic pain is frequently accompanied by many comorbid psychiatric symptoms, including depression and anxiety (36-38). Although individual difference research in chronic pain is in its infancy, it is important—and in keeping with recent calls for “personalized medicine” (e.g., (39))—to investigate what factors predict response to different psychosocial treatments. In the literature, higher baseline depression scores predicted greater pain reduction among adults with chronic musculoskeletal pain who completed EAET (23). In addition, in our pilot work, higher baseline anxiety was also associated with greater pain reduction for EAET patients. One possible explanation for these findings is that patients who report higher anxiety or depression, or patients who express greater emotional distress, may be more able to readily access and work with the affective components of pain, which provides the substrate that is amenable to this emotion-focused therapeutic modality.

In contrast, some data suggest that patients with high emotional distress, using measurements of anxiety and depressive symptoms, may have less likelihood of benefit from CBT for chronic pain (15). Theoretically, this may be explained because patients in less emotional distress may be more amenable to learning cognitive and behavioral coping skills in CBT and less capable of working with a treatment such as EAET, which requires ready access to emotions. Thus, this research will investigate these theoretical and empirical findings in our population by examining whether patients with higher emotional distress at baseline—depression or anxiety—have stronger benefits from EAET on primary and secondary outcomes, and Veterans who express lower baseline emotional distress have stronger benefits from CBT.

The measurement of emotional distress commonly uses assessments of depression and anxiety as proxies for distress, such as in the Patient-Reported Outcomes Measurement Information System (PROMIS), which relied on comprehensive literature searches and qualitative item analysis to define item banks for depression and anxiety to, in part, represent emotional distress (40).

Two Interventions with Largely Distinct Mechanisms of Action to Influence the Central Nervous System Aspects of Chronic Musculoskeletal Pain:

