In spite of these distinct hypothesized mechanisms of action, both CBT and EAET are proposed to share some mechanistic qualities. For instance, both psychodynamic treatments and CBT are hypothesized to operate, in part, through the strength of the working alliance (64, 65). Thus, the proposed research also tests whether response to both treatments is mediated by a positive working alliance.

Significance of the Proposed Research:

Given the limited efficacy of available psychosocial treatments for chronic pain and the recent opioid crisis, it is vital that novel approaches be developed and tested. There is substantial evidence that emotional avoidance resulting from failure to process stressful experiences and their accompanying emotions contribute to the pain and symptoms of many individuals with chronic pain, suggesting the need for a treatment such as EAET that largely targets these processes. Thus, the proposed research holds substantial promise to advance clinical practice and treatment outcomes, as well as theory and future research.

As suggested by theory, empirical research, and our pilot data, an EAET approach has great potential to improve the health of older Veterans with chronic musculoskeletal pain, thus filling a gap in current pharmacologic, physical, and cognitive-behavioral approaches. This research can make available an innovative, empirically-supported therapy, including a written protocol, for use in treating these Veterans. Comparing EAET to a standard intervention is key to determining whether the innovative EAET approach is superior to what is currently available, and also whether different subsets of older Veterans, such as those with different levels of emotional distress, respond to these two different interventions. If these aims are supported, then our ability to tailor interventions for specific patients, or match Veterans to optimal treatments, will be greatly enhanced. Furthermore, the strong recruitment of racial/ethnic minorities in our pilot work is a further strength of this research, which will focus on a multi-ethnic/multi-racial Veteran population and the importance of understanding and improving treatment approaches across Veterans of all races and ethnicities.

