5.7 Data Analysis

Statistical Plan:

The experimental design for this study is a 2-group randomized superiority trial, with assessments at baseline, post-treatment (primary endpoint), and 6-month follow-up. The aims correspond to comparisons of the effects of two active treatments to each other (Aim 1), moderation of the interventions (Aim 2), and mediation of the interventions (Aim 3).

Prior to performing the primary analyses, descriptive statistics and graphical summaries are obtained for all outcomes to check for missing data, outliers, and the need for transformations or non-parametric methods.

To assess the success of randomization, continuous baseline covariate statistics will be reported and compared with p-values computed using the t-test or the nonparametric analog (Wilcoxon rank sum test). The p-values for comparing categorical baseline covariates will be computed using chi-square tests or the nonparametric analog (Fisher's exact test). We will compare primary pain and secondary outcomes, demographic (age, race/ethnicity, marital status, education) and clinical (number of medical conditions, presence of psychiatric disorder, presence of substance use, presence of opioid medications) characteristics. While we will not anticipate imbalance in a randomized trial, baseline factors that are clinically and statistically significant and are thought or shown to have a nontrivial effect on the pain change or other outcomes will be considered as adjustment factors. If adjustments are needed, both unadjusted and adjusted results will be reported.

Aim 1: Treatment Group Comparisons: The general linear mixed model (GLMM) will be used to compare BPI mean pain severity changes from baseline and other secondary continuous outcomes between the two groups (EAET, CBT) over time in order to account for correlations induced by repeated measures within subjects and allow for both fixed and time-varying covariates. For ease of interpretation, change from baseline is used as the outcome instead of modeling post-treatment pain with baseline pain as an additional predictor. The GLMM produces consistent estimates when there are missing data if the data are missing at random (MAR). Group, time, and the group x time interaction will be evaluated accounting for correlations via random person effects. Analyses will be carried out via intent to treat (ITT). The primary analyses will use all data.

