If an adjusted analysis is needed, we will use logistic regression of treatment group versus the selected covariates to create a propensity score. This score will then be used as an added covariate in the GLMM or will be used to create adjustment strata if the association of pain change with the propensity score is nonlinear or not easily modelled.

Aim 2: Moderation of the Interventions. We hypothesize that patients with higher baseline depression and anxiety will experience greater pain reduction from EAET relative to CBT, whereas those with lower baseline depression and anxiety will benefit more from CBT relative to EAET. To test moderation of condition effects by these baseline characteristics, we will use the PROCESS macro developed by Hayes (92). This approach, which is based on the most current statistical considerations for model testing, involves bootstrapped analyses and estimates of various prespecified models, including tests of both moderators and mediators (92). We will examine depression and anxiety separately to test our hypotheses, but we will also explore, using principal components analysis, whether depression and anxiety should be combined into a composite. Significant interactions will be plotted for post-hoc probing, and high and low values (e.g., ± 1 SD from the sample mean) will be plotted. We also will examine cut-scores on the moderators to classify participants into subgroups that are responsive or amenable to each intervention—an approach that can facilitate later tailoring or treatment matching. For exploratory purposes, we will carry out the same analyses for the secondary outcome measures as well.

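### The Aim 2 moderation model names no baseline pain term: this costs some precision and leaves a distress effect that cannot be told apart from a pain-severity effect

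*Combined protocol and SAP*

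**What the plan says.** The Aim 2 paragraph of section 5.7 sets out the test: "To test moderation of condition effects by these baseline characteristics, we will use the PROCESS macro". It says this approach "involves bootstrapped analyses and estimates of various prespecified models, including tests of both moderators and mediators", but writes none of those models out. The moderators are baseline PROMIS depression and anxiety: "We will examine depression and anxiety separately to test our hypotheses". Plots at one SD either side of the mean and a search for cut-scores follow. No covariate is named.

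Baseline pain is mentioned as a possible predictor only under Aim 1, where "change from baseline is used as the outcome instead of modeling post-treatment pain with baseline pain as an additional predictor". Covariate adjustment is also described before Aim 2. It is reserved for "baseline factors that are clinically and statistically significant and are thought or shown to have a nontrivial effect" after a comparison of the arms, and it takes the form of a propensity score: "This score will then be used as an added covariate in the GLMM" (or strata). That route depends on imbalance between arms and contains no product of arm and baseline pain.

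Section 2.0 states that "Chronic pain is frequently accompanied by many comorbid psychiatric symptoms, including depression and anxiety". It also says that if the aims are supported, "our ability to tailor interventions for specific patients, or match Veterans to optimal treatments, will be greatly enhanced". Baseline BPI severity is collected from every participant (section 5.5, Table 2).

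**The concern.** Baseline pain usually predicts change in pain, because high scores tend to fall and low scores to rise. Leaving it out of a model of change puts that predictable variation into the residual and widens the interval for the arm-by-distress term.

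The second issue is interpretation. Section 2.0 offers a specific reason why distress should matter: distressed patients have readier access to the emotions that EAET works on. If EAET's advantage over CBT is larger in patients with worse pain, and those patients are also more distressed, an arm-by-distress interaction will appear without that mechanism. Section 5.4 sets no minimum pain severity, so baseline pain may vary widely. At stake are the support that a positive result lends to the emotion-access theory, and the choice of variable for later matching. If pain severity were the driver, a distress cut-score would be the weaker tool.

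**Working it through.** **The plan's own Aim 2 figure.** The stated 80% power for r = 0.35 with n = 60 is for a correlation within one arm. Fisher's z gives atanh(0.35) × √57 − 1.960 = 0.365 × 7.550 − 1.960 = 0.80, so power is 78.8%, in line with the plan. That calculation involves neither the arm-by-distress term nor baseline pain.

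**Inputs from the documents.** There are 60 completers per arm. The SD of change is not stated, but 0.70 points at 80% power implies 0.70 / [(1.960 + 0.842) × √(2/60)] = 1.37; the simulations below used 1.36, an immaterial difference. The mean EAET advantage is taken as 0.70 (the detectable difference in section 5.7) or 1.44 − 0.39 = 1.05 (the pilot difference in section 2.0).

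**Assumed, not in the documents.** Mean baseline BPI is 5.5 and its SD 1.5 to 2.2. The pain-distress correlation ρ is 0.3 to 0.5. BPI variance is equal before and after CBT. For the second calculation only, the EAET advantage is proportional to baseline pain and distress has no effect of its own.

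**1. Precision.** With equal variances, baseline pain explains a share 1.36² / (4 × SD²) of the variance of change.
- At SD 1.8 this is 1.85 / 12.96 = 14%. Over SD 2.2 to 1.5 it is 10% to 21%.
- The standard error (SE) of the arm-by-distress term, per SD of distress, is about σ × √(2/60). Without baseline pain it is 1.36 × 0.183 = 0.25. With it, σ = 1.36 × √0.857 = 1.26 and the SE is about 0.23 (0.24 in simulation).
- For a true moderation of 0.6 points per SD, simulated power is about 66% without baseline BPI and 70-72% with it. As a check by hand, 0.6/0.24 − 1.96 = 0.54, which is 71%.

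**2. How much pain severity can pass into the distress term.** The EAET advantage changes by δ × SD / 5.5 per SD of baseline pain. Distress picks up ρ times that.

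| δ | baseline SD | ρ | ρ × δ × SD / 5.5 |
|---|---|---|---|
| 0.70 | 1.5 | 0.3 | 0.06 |
| 0.70 | 2.2 | 0.5 | 0.14 |
| 1.05 | 1.8 | 0.3 | 0.10 |
| 1.05 | 1.8 | 0.5 | 0.17 |

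Against an SE near 0.25 these shifts are small. In simulation (t-tests in place of bootstrap intervals), the arm-by-distress term reached p < 0.05 in 8.5% of trials in the second row and 9.7% in the fourth.

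**3. Which term separates the two explanations.** Baseline BPI as a covariate alone does not: the same two settings give 8.9% and 11.3%. Adding arm by baseline BPI brings the second row to about 5.6%, and the mean arm-by-distress estimate falls to zero. If the advantage does not scale with pain, or ρ = 0, there is nothing to separate.

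**4. Cost of the product term.** It multiplies the variance of the arm-by-distress estimate, relative to the covariate model, by 1/(1 − ρ²): 1.10 at ρ = 0.3 and 1.33 at ρ = 0.5. Power in the example becomes about 58-67%, against 70-72% with the covariate alone.

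**The case against.** The strongest reply is that Aim 2 asks who benefits. Arm is randomised, so the unadjusted arm-by-distress term properly estimates how the EAET-CBT difference varies with distress, whatever the reason. If the advantage scales with pain and distress tracks pain, benefit really does differ by distress. A reader might infer from the rejection rates above that the test has an inflated type I error. The documents do not support that for the question Aim 2 mainly poses. The excess is a false positive only for the narrower claim that distress moderates independently of pain. This objection stands.

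The premise is also assumed. The percentage reductions in section 2.0 describe responders and do not show that the arm difference scales with baseline pain; the same section reports absolute points as well. No pain-distress correlation is given. The pilot correlations of anxiety with pain change, −0.40 under EAET and +0.53 under CBT (section 5.7), do not fit pain scaling alone. Under the assumptions above, the CBT correlation would be −ρ × 1.36 / (2 × SD), between −0.09 and −0.23. The pilot pair implies roughly 0.93 × 1.36 = 1.3 points per SD, far beyond 0.17. Pain scaling is therefore unlikely to be the whole explanation, though pilot correlations are imprecise. This too stands.

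Two further readings go too far. The plan does not rule baseline pain out of Aim 2: it is silent, and the explicit omission is written for Aim 1. Nor is any Veteran matched to treatment in this trial; matching is described as a later and conditional use.

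What remains is that the model is not written out, a useful covariate already in hand is not named, and nothing planned separates distress from pain severity.

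**Conclusion.** The point holds as one of precision and attribution, not of validity. Naming baseline BPI would lift power by about 4 to 6 percentage points in the example (66% to 70-72%), given the assumed baseline SD of 1.8, moderation of 0.6 points per SD and equal variances. The part of an arm-by-distress estimate that could reflect pain severity is about 0.06 to 0.17 points per SD of distress. This requires an EAET advantage proportional to baseline pain and a pain-distress correlation of 0.3 to 0.5, neither of which the documents establish. A significant result from the planned test would support calling distress a marker of who benefits on average. It would not by itself support the explanation in section 2.0 that distress is what makes EAET work better. The change is worth making because it costs almost nothing; the plan is not unsound without it.

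**What to change.** In the Aim 2 paragraph of section 5.7, write the model out and enter baseline BPI severity as a covariate in the Aim 2 models of pain change. Its purpose there is precision. Prespecify one sensitivity model for each moderator that adds arm by baseline BPI severity, and report the arm-by-distress estimate with its confidence interval from both models. State that moderation will be attributed to distress itself, as opposed to distress as a marker of who benefits, only with reference to the second model.

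The cost is a few sentences and one extra model per moderator on data already collected. The second model estimates the arm-by-distress term less precisely than the covariate model (power about 58-67% in the example). It should be labelled an attribution check and not the main test, and a wider interval there should not be read as evidence against moderation.

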The proposed randomized clinical trial tests the hypothesis that EAET is superior to CBT on reduction in mean pain severity and other outcomes derived from IMMPACT. To examine which patients are most likely to benefit, this research also tests whether greater baseline emotional distress (using measures of anxiety and depression) predicts stronger benefits from EAET and whether lower baseline emotional distress predicts stronger benefits from CBT. Finally, this research explores whether the benefits of EAET are mediated by improved emotion regulation the benefits of CBT are mediated by improved cognitive and behavioral coping, and whether the benefits of both are mediated by a stronger working alliance. We plan to enroll 160 multi-ethnic/multi-racial older Veterans (age 60-95 years) with chronic musculoskeletal pain at the West Los Angeles VA Medical Center.

This research can introduce an additional, potentially more effective format of psychotherapy at VA so that more Veterans with chronic pain can respond. In addition, this research can lead to better treatment targeting and enhance our understanding of how psychotherapy treatments work. Finally, this research can facilitate the development of critical skills for the PI in psychotherapy research and pain management and enhance his ability to effect positive change for older Veterans.

List of Abbreviations:

AAGP – American Association for Geriatric Psychiatry
APA – American Psychoanalytic Association
APS – American Psychosomatic Society
ACOS/R – Associate Chief of Staff for Research
ACT – Acceptance and Commitment Therapy
BPI – Brief Pain Inventory
CBT – Cognitive Behavior Therapy
CBT-CP – Cognitive Behavior Therapy for Chronic Pain
CDA – Career Development Award
CDC – Centers for Disease Control and Prevention
CSR&D – Clinical Science Research and Development
DoD – Department of Defense
EAET – Emotional Awareness and Expression Therapy
EBP – Evidence-Based Psychotherapy
ECT – Electroconvulsive Therapy
EMG – Electromyography
fMRI – Functional Magnetic Resonance Imaging
GLMM – General Linear Mixed Model
GPOP – Geriatric Psychiatry Outpatient Program
HIPAA – Health Insurance Portability and Accountability Act
IBM – International Business Machines Corporation
IMMPACT – Initiative on Methods, Measurement, and Pain Assessment in Clinical Trials
IEDTA – International Experiential Dynamic Therapy Association
IPA – International Psychoanalytical Association
IRB – Institutional Review Board

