3.0 Objectives

The Specific Aims for this study are:

Aim 1: Main Effects. Test the hypothesis that EAET is superior to VA standard treatment (CBT) in 160 older Veterans (age 60-95 years) with chronic musculoskeletal pain on the following PCO:

- a. **Primary outcome:** change in mean pain severity baseline to post-treatment.

b. **Secondary outcomes:** change in pain interference, mood, anxiety, PTSD symptoms, meaning/purpose, sleep disturbance, fatigue, patient global impression of change, and patient satisfaction baseline to post-treatment and baseline to 6-month follow-up and change in mean pain severity baseline to 6-month follow-up.

Aim 2: Moderation of the Interventions. Test the hypothesis that EAET will have stronger benefits for patients who express more baseline emotional distress (using greater depression and anxiety as proxies for emotional distress), whereas CBT will have stronger benefits for patients who express less baseline emotional distress (using greater depression and anxiety as proxies).

Aim 3: Mediation of the Interventions. Explore hypotheses that the benefits of EAET are mediated by improved emotion regulation (as reflected in several measures of emotion regulation), the benefits of CBT are mediated by improved cognitive and behavioral coping (as reflected in several measures of coping), and both interventions are mediated by a positive working alliance.

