5.0 Study Procedures

5.1 Study Design

The project is a randomized superiority trial that compares change in mean pain severity and other outcomes in older Veterans (age 60-95 years) with chronic musculoskeletal pain who receive either Emotional Awareness and Expression Therapy (EAET) or Cognitive Behavior Therapy (CBT). The study includes 160 total participants, 80 randomly assigned to EAET and 80 to CBT. Each participant receives one 90-minute individual session and eight 90-minute group sessions based on the treatment condition (EAET or CBT) to which he/she is randomly assigned. Each EAET group at a time runs concurrently with one CBT group throughout the study. Group sessions consist of small groups of eight Veterans. All participants complete self-report questionnaires on pain, physical and psychiatric symptoms, and emotional well-being at baseline, post-treatment, and 6-month follow-up. Participants also complete self-report questionnaires on emotional approach coping, ambivalence over emotional expression, pain catastrophizing, and adaptive pain coping skills at baseline, post-treatment, and 6-month follow-up. Participants complete a working alliance questionnaire at post-treatment. The data are used to assess the superiority of EAET compared to CBT on change in mean pain severity scores from baseline to post-treatment (primary outcome) and 6-month follow-up and change in other patient-centered outcomes (PCO) from baseline to post-treatment and 6 month-follow-up (secondary outcomes). In addition, the data are used to test mediation of EAET by improved emotion regulation (greater emotional approach coping and decreased ambivalence over

emotional expression), mediation of CBT by improved cognitive and behavioral coping (decreased catastrophizing and increased pain coping skills), and mediation of both treatments by strength of the working alliance. Finally, the data are used to test whether higher baseline depression and anxiety predict response to EAET and lower baseline depression and anxiety predict response to CBT.

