Aim 3 (Exploratory): Mediation of the Interventions. This aim pertains to the potential mediating effects of ambivalence over emotional expression and emotional approach coping on the effects of EAET, of pain coping and catastrophizing on CBT, and working alliance on both EAET and CBT. For primary and secondary outcomes at post-treatment, we will test the potential mediators that are assessed concurrently. For the 6-month follow-up evaluation, we will test both the post-treatment and the 6-month follow-up (concurrent) mediators. We will examine the mediators separately, but we also will use multivariate methods (principal component scoring algorithm) to explore whether the potential mediators for each intervention should be combined into composites. We will assess mediation by also using the PROCESS macro developed by Hayes (92, 93).

Sample Size and Power Considerations:

Aim 1: Data from our first two pilot groups showed a mean 1.13-point improvement in BPI mean pain severity under EAET compared to a 0.33-point mean improvement of BPI mean pain severity under CBT, a mean difference of $1.13 - 0.33 = 0.80$ points. Using a sample size of $n = 60$ per group and assuming the same SDs, there is 80% power to confirm mean differences as small as 0.70 points using the usual two-sided $\alpha = 0.05$ significance level. In our pilot, only six of 32 participants were lost to follow-up after

completing baseline assessments and randomization. We estimate at least this dropout rate for the proposed study and possibly up to 25% of participants (based on previous studies, e.g., (16)). We therefore will need to enroll at least $60/0.75 = 80$ participants per group or 160 participants total.

Aim 2: A sample size of $n = 60$ has 80% power ($\alpha=0.05$) for confirming correlations as small as $r = 0.35$ (in absolute value) using the usual $\alpha = 0.05$ significance level. Our pilot data shows that the correlation between anxiety and pain change in the EAET group was $r = -0.40$, and the correlation between anxiety and pain change in the CBT group was $r = 0.53$, both well within this margin. Based on the findings of Burger, et al. (23), we anticipate a possibly larger correlation between depression and reduction in pain than found in our pilot groups. We believe that correlations between pain severity change and depression and anxiety also may be even larger, given the large variation in the pilot sample.

Dropouts:

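### Aim 2's 80% power is for a correlation within one arm; no power is given for the planned arm-by-distress interaction or for CBT beating EAET at low distress

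*Combined protocol and SAP*

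**What the plan says.** Section 5.7, under sample size and power, gives one power figure for Aim 2: n = 60 has 80% power at alpha 0.05 "for confirming correlations as small as $r = 0.35$ (in absolute value"). It supports this with pilot correlations between anxiety and pain change, given separately by arm: -0.40 in EAET and 0.53 in CBT.

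The Aim 2 analysis text in the same section describes a different test: "To test moderation of condition effects by these baseline characteristics, we will use the PROCESS macro". Significant interactions are then probed, and "high and low values (e.g., ± 1 SD from the sample mean) will be plotted". The hypothesis is comparative in both directions. High-distress patients gain more from EAET than from CBT, "whereas those with lower baseline depression and anxiety will benefit more from CBT relative to EAET".

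Elsewhere the CBT half appears without the comparison with EAET:

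- Abstract: "whether lower baseline emotional distress predicts stronger benefits from CBT"
- Section 2.0: "Veterans who express lower baseline emotional distress have stronger benefits from CBT"
- Section 3.0: "whereas CBT will have stronger benefits for patients who express less baseline emotional distress"
- Section 5.1: "lower baseline depression and anxiety predict response to CBT"

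Section 5.5 words it in a similar way.

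**The concern.** A correlation within one arm asks whether distress predicts change in that arm. An interaction asks whether the slope differs between arms, so its power depends on both slopes and on the sampling error of both. The claim that low-distress patients do better on CBT is a third question: whether the treatment difference at a low distress value lies on the CBT side of zero. The stated 80% answers only the first.

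Two things are at stake. A reader would take 80% as the power of the Aim 2 test, when the true figure may be higher or lower. And a significant interaction could be taken to confirm that CBT is better at low distress, when it may show only that EAET's advantage shrinks there. The plan calls for plots at high and low distress, and cut-scores to support treatment matching, but gives no rule for when CBT counts as better.

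**Working it through.** **Inputs from section 5.7.** 60 completers per arm; alpha 0.05 (two-sided is stated for Aim 1 and assumed here); pilot correlations -0.40 (EAET) and 0.53 (CBT); pilot mean difference 1.13 - 0.33 = 0.80 points in favour of EAET; Aim 1 detectable difference 0.70 points at 80% power. Change is taken as post-treatment minus baseline, so a negative r means more pain reduction with more distress.

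**Assumed.** Equal SDs of change in both arms, independent patients, one moderator tested at 0.05.

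**1. The plan's own figure.** Power = Φ(atanh(r)·√(n - 3) - 1.96).

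- n = 60, r = 0.35: Φ(0.365 × 7.550 - 1.96) = Φ(0.80) = 78.8%. A noncentral t calculation gives 81.2%. The stated 80% reproduces.
- n = 120 would give 97.7%, so the figure fits one arm and not both arms together.

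**2. The interaction.** Power = Φ(|atanh(rE) - atanh(rC)| / √(2/57) - 1.96), with √(2/57) = 0.187. The last column simulates the regression slope-difference test (40,000 runs).

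| rE / rC | Gap in z | Formula | Simulation |
|---|---|---|---|
| -0.40 / 0.53 (pilot) | 1.014 | >99.9% | >99.9% |
| -0.35 / +0.35 | 0.731 | 97.4% | 97.5% |
| -0.20 / 0.265 (half pilot) | 0.474 | 71.6% | 71.9% |
| -0.35 / 0 | 0.365 | 49.6% | 48.5% |

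For 80% power, correlations of -0.255/+0.255 give 79.7% by simulation. The detectable slope difference is therefore about 0.51 SD of change per SD of distress. That is 0.51 × 1.36 = 0.69 points at the SD derived in step 3.

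Unequal SDs matter in the marginal case. With assumed SDs of 1.7 and 0.9, power at -0.35 against 0 is 69% if EAET has the larger SD and 24% if CBT has. At the pilot correlations it stays above 99% either way.

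**3. SD of change.** Not stated. A 0.70-point difference at 80% power with 60 per arm (two-sample t) implies an SD of 1.357.

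**4. CBT better than EAET at k SD below mean distress.** Expected CBT advantage = -0.80 + (rC - rE)·SD·k; SE = √(SD²·[(1 - rE²) + (1 - rC²)]·(1 + k²)/60).

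- Pilot correlations, SD 1.357, k = 1: advantage = -0.80 + 0.93 × 1.357 = 0.462. SE = √(1.841 × 1.559 × 2/60) = 0.309. Power = Φ(0.462/0.309 - 1.96) = 32%.
- SD 1.0: advantage 0.13, power 8%. SD 2.0: advantage 1.06, power 64%. Simulation gives 32.5%, with 9% and 61% at the two ends.
- k = 1.5: about 75% by simulation (51% to 90% over the same SDs).

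The expected crossing point is 0.80/(0.93 × 1.357) = 0.63 SD below the mean. At -1 SD, CBT has little room to show an advantage.

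**The case against.** The strongest reply is that on the plan's own assumptions the interaction is well powered. The pilot correlations have opposite signs, and both exceed 0.35 in size. At those values, and even at -0.35/+0.35, interaction power is well above 80%, so the stated figure is conservative. This stands. A reader might infer from the mismatch that the interaction is underpowered, or that the power calculation contains an error. The documents support neither: the figure reproduces, and the 50% case needs distress not to predict CBT response, contrary to the hypothesis. It is a sensitivity case. It still shows that an EAET correlation at the stated threshold does not by itself secure 80% power for the planned test.

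It can also be said that the 32% is fragile. It needs an SD that the documents do not give, it takes pilot values at face value, and it uses -1 SD, which the plan offers only as an example for plotting. This also stands, and is why the range and the -1.5 SD result are given. The direction does not depend on the exact value: the average EAET advantage must be overcome before CBT can be better.

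Finally, a reader might infer from the differing wordings that the protocol holds two competing versions of Aim 2. The analysis section states the comparison explicitly, and the other places read as summaries. Harmonising them is tidy but optional.

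**Conclusion.** The point holds as a mismatch of power basis and test. The 80% at |r| = 0.35 is correct for a single-arm correlation and is not the power of the interaction or of the low-distress comparison. With 60 per arm, two-sided 0.05, equal SDs, no therapy-group correlation and one moderator, interaction power runs from above 99% at the pilot correlations to about 50% at -0.35 against 0.

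The low-distress contrast is the weaker part. At the pilot correlations, where the interaction is almost certain to be significant, CBT would be shown better at -1 SD in about a third of trials if the SD of change is 1.36. A significant interaction therefore does not establish the low-distress half of the hypothesis. The point is worth correcting because section 3.0 sets Aim 2 as a hypothesis to be tested and section 5.7 labels only Aim 3 exploratory as a whole. The primary aim and the sample size are untouched.

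**What to change.** 1. Replace the Aim 2 power sentence with text such as: *The Aim 2 test is the arm-by-distress interaction in the regression of BPI change. With 60 per arm and two-sided 0.05, power is 80% for a slope difference of about 0.51 SD of change per SD of distress, assuming equal SDs of change in both arms, no correlation within therapy groups and one moderator tested at 0.05. The r = 0.35 figure applies to a correlation within one arm only.* Recompute if the pilot SDs differ by arm.
2. Add to the probing step: *CBT will be called better at low distress only if the 95% CI for the EAET-CBT difference in BPI change, at a prespecified low-distress value (for example -1 SD), lies wholly on the CBT side of 0.* State that contrast's power over a range of SDs. Otherwise, word the hypothesis as an EAET advantage that grows with distress.
3. Optionally, bring the abstract and sections 2.0, 3.0, 5.1 and 5.5 into line with section 5.7.

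The cost is a few sentences and one prespecified contrast, with no extra patients or data. The downside is that the low-distress claim either carries a lower stated power, which depends on the SD used, or is worded more narrowly.
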